4.3.2 Secondary endpoints

4.3.2.1 Alive and free of respiratory failure at Day 14

The point estimate and its 90% confidence interval (CI; using Wald method with continuity correction) will be calculated for each treatment group. Summaries of the subgroups specified in Section 4.3.1.1 will also be produced. Analyses may be repeated for the PPAS, using the definition of the PPAS in Section 3.1.2.

The proportion for each group, and the difference in proportions, as well as the 90% CIs, will also be reported in the FAS but excluding subjects who have withdrawn or have been lost to follow-up on or prior to Day 28.

The number and percentage of subjects who experienced respiratory failure but were free of respiratory failure at Day 14 will be summarized by treatment group. This summary will also include summary statistics for the number of respiratory failures that occurred.

The method for handling subjects that withdraw or are lost to follow up on or prior to Day 14 is detailed in Section 3.1.2.

4.3.2.2 Percent change from baseline in C-reactive protein

Summary statistics (n, mean, median, SD, minimum, and maximum) and the percent change from baseline to each scheduled study assessment will be presented by treatment group.

Box plots of absolute value over time and a line graph of mean change (and SD) from baseline to each scheduled study assessment may be presented for each treatment group.

A by-subject listing will also be presented.

4.3.2.3 Change from baseline in ferritin

Summary statistics (n, mean, median, SD, minimum, and maximum) and the change and percent change from baseline to each scheduled study assessment will be presented by treatment group.

Box plots of absolute value over time and a line graph of mean change (and SD) from baseline to each scheduled study assessment may be presented for each treatment group.

A by-subject listing will also be presented.

4.3.2.4 Change from baseline in absolute lymphocyte count

Summary statistics (n, mean, median, SD, minimum, and maximum) and the change and percent change from baseline to each scheduled study assessment will be presented by treatment group.

Box plots of absolute value over time and a line graph of mean change (and SD) from baseline to each scheduled study assessment may be presented for each treatment group.

A by-subject listing will also be presented.

4.3.2.5 All-cause mortality at Day 90

The number and percentage of subjects who have died (all-cause and ‘related to disease under investigation’ as recorded in the DEATH eCRF), those still alive, those with unknown survival status (lost to follow-up), those who have withdrawn consent and those censored for any other reason at Day 90 will be summarized by treatment group.

Kaplan-Meier (KM) plots and summary statistics will be presented for survival time by treatment group. The proportion of subjects alive at Day 90 will be defined as the KM estimate of overall survival at 90 days. This will be presented, along with its 90% CI. The computation of the CI will be based on a log-log transformation.

The method for handling subjects that withdraw or are lost to follow up on or prior to Day 90 is detailed in Section 3.1.6.

Subgroup analyses on COVID-related deaths may be performed as appropriate.

4.3.2.6 Alive and discharged from the ICU at Days 14 and 28

A summary of the number and percentage of subjects alive and discharged from the ICU at Day 14 will be presented. This will be repeated for Day 28. Analyses may be repeated for the PPAS, using the definition of the PPAS in Section 3.1.7.

The method for handling subjects that withdraw or are lost to follow up on or prior to Day 14 (or Day 28) is detailed in Section 3.1.7.

4.3.2.7 Time to first occurrence of respiratory failure or death

Time from randomization to first occurrence of respiratory failure or death (due to any cause) on study (up to Day 28), whichever occurs first, will be analyzed using the KM method by treatment group.

KM plots and summary statistics will be presented for time to first occurrence of respiratory failure or death by treatment group.

The HR and its 90% CI will be estimated from a stratified Cox Proportional Hazards model (with ties = Efron), stratified by age (<65 vs ≥65 years) and comorbidities (present vs absent). The CI calculated using a profile likelihood approach. Summary statistics will include the lower and upper quartile and median survival time with 90% CI.

The method for handling subjects that withdraw or are lost to follow up is detailed in Section 3.1.8.

4.3.2.8 Days alive and free of respiratory failure over the course of 28 days

Summary statistics (n, mean, median, SD, minimum, and maximum) of the number of days alive and free of respiratory failure over 28 days will be presented by treatment group. In addition, the number and percentage of subjects in the following categories will be presented, 0 days, 1-6 days, 7-14 days, 15-21 days, and 22-28 days.

The method for handling subjects that withdraw or are lost to follow up on or prior to Day 28 is detailed in Section [3.1.9](#).

4.3.2.9 Days with respiratory failure over the course of 28 days

Summary statistics (n, mean, median, SD, minimum, and maximum) of the number of days with respiratory failure over 28 days will be presented by treatment group. In addition, the number and percentage of subjects in the following categories will be presented, 0 days, 1-6 days, 7-14 days, 15-21 days, and 22-28 days.

A bar chart of the number of days with respiratory failure for each subject within the treatment group will be produced, i.e., showing graphically the distribution of the number of days with respiratory failure for each treatment group.

The proportion of subjects who experienced respiratory failure or died over the course of 28 days will also be summarized by treatment group. Subjects with respiratory failure on the day of randomization will be excluded from this summary.

Furthermore, the proportion of subjects who required invasive ventilation or ECMO or died over the course of 28 days will be summarized by treatment group.

The method for handling deaths and subjects that withdraw or are lost to follow up on or prior to Day 28 is detailed in Section [3.1.10](#).

4.3.2.10 Days hospitalized over the course of 28 days

Summary statistics (n, mean, median, SD, minimum, and maximum) of the number of days hospitalized over 28 days will be presented by treatment group. In addition, the number and percentage of subjects in the following categories will be presented, 0 days, 1-6 days, 7-14 days, 15-21 days, and 22-28 days.

A bar chart of the number of days hospitalized for each subject within the treatment group will be produced, i.e., showing graphically the distribution of the number of days hospitalized for each treatment group.

The method for handling deaths and subjects that withdraw or are lost to follow up on or prior to Day 28 is detailed in Section [3.1.113.1.8](#).

4.3.2.11 Days in ICU over the course of 90 days

Summary statistics (n, mean, SD, median, minimum and maximum) for the length of stay (days) in ICU over 90 days will be presented by treatment group. In addition, the number and

percentage of subjects in the following categories will be presented, 0 days, 1-6 days, 7-14 days, 15-21 days, 22-28 days and >28 days.

A bar chart of the number of days in ICU for each subject within the treatment group will be produced, i.e., showing graphically the distribution of the number of days in ICU for each treatment group.

The method for handling deaths and subjects that withdraw or are lost to follow up on or prior to Day 90 is detailed in Section 3.1.12.

4.3.2.12 Days alive outside of hospital over the course of 28 days

Summary statistics (n, mean, SD, median, minimum and maximum) of the days alive outside of hospital over 90 days will be presented by treatment group.

The method for handling subjects that withdraw or are lost to follow up on or prior to Day 28 is detailed in Section 3.1.13.

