3. OBJECTIVES AND ENDPOINTS

Pr	imary Objectives	Primary Endpoints/Variables
•	To evaluate the safety of acalabrutinib in subjects with COVID-19 when administered with BSC	 Safety Type, frequency, severity, and relationship to study treatment of any TEAEs or
•	To evaluate the efficacy of adding acalabrutinib to BSC for the treatment of COVID-19	abnormalities of laboratory tests, SAEs, or AEs leading to discontinuation of study treatment. Efficacy
		 Proportion of subjects alive and free of respiratory failure at Day 28
		 For the purpose of this study, respiratory failure, is defined based on resource utilization of any of the following modalities: (a) Endotracheal intubation and mechanical ventilation
		(b) Oxygen delivered by high-flow nasal cannula (heated, humidified, oxygen

Table 3Protocol Objectives and Endpoints

	 delivered via reinforced nasal cannula at flow rates >20 L/min with fraction of delivered oxygen ≥0.5) (c) Noninvasive positive pressure ventilation or continuous positive airway pressure (d) Extracorporeal membrane oxygenation
Secondary Efficacy Objective	Secondary Efficacy Endpoints/Variables:
To evaluate the efficacy of adding acalabrutinib to BSC for the treatment of COVID-19	 Proportion of subjects alive and free of respiratory failure (as defined above) at Day 14 Demonstration from baseling in CDD (time)
	• Percent change from baseline in CRP (time frame: baseline, Days 3, 5, 7, 10, 14, 28)
	• Change from baseline in ferritin (time frame: baseline, Days 3, 5, 7, 10, 14, 28)
	• Change from baseline in absolute lymphocyte counts (time frame: baseline, Days 3, 5, 7, 10, 14, 28)
	• All-cause mortality at Day 90
	• Proportion of subjects alive and discharged from the ICU at Days 14 and 28
	• Time from randomization to first occurrence of respiratory failure or death on study (up to 28 days after randomization) due to any cause
	• Number of days alive and free of respiratory failure from randomization to 28 days after randomization
	• Number of days with respiratory failure from randomization to 28 days after randomization
	• Number of days hospitalized from randomization to 28 days after randomization
	• Number of days in ICU (length of stay) from randomization to 90 days after randomization
	• Number of days alive outside of hospital from randomization to 28 days after randomization
	• Number of days alive outside of hospital from randomization to 90 days after randomization

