9.6.2 Efficacy Analyses

Primary Endpoint

The primary endpoint is the proportion of subjects who are alive and free of respiratory failure at Day 28 (see Section 3 for a definition of respiratory failure). The point estimate and its 90% confidence interval (CI; using Wald method with continuity correction) will be calculated for each treatment arm. The Cochran-Mantel-Haenszel χ^2 test stratified by age ($\geq 65 \text{ vs} < 65 \text{ years}$) and comorbidities (present vs absent) will be used to compare the proportion of subjects who are alive and free of respiratory failure at Day 28 between the two treatment arms. An unstratified analysis will also be performed. Finally, the difference in the proportion of subjects who are alive and free of respiratory failure at Day 28 will also be

provided with 90% CIs. The treatment difference will be also estimated using a logistic regression (Ge 2011) with indicators for treatment and the randomization stratification factors (2×2) as well as baseline respiratory failure (with vs without).

The primary endpoint of the study will be summarized by subgroups that include age group, sex, race, ethnicity, comorbidities, baseline respiratory failure, and history of substance abuse.

The primary endpoint will be summarized and analysed as per the methods above for the full analysis set (ITT population) as well as the per-protocol analysis set.

Additional sensitivity analyses and subgroup analyses of the primary endpoint may be performed as appropriate.

Secondary Endpoints

The proportion of subjects alive and free of respiratory failure at Day 14 will be summarized using the full analysis set.

Summary statistics (n, mean, median, standard deviation, minimum, and maximum) will be presented by treatment arm for continuous secondary efficacy endpoints (refer to Section 3). Summary statistics for the number of days hospitalized from randomization to 28 days after randomization and the number of days in ICU from randomization to 90 days after randomization will be summarized.

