3.1.13 Days alive outside of hospital over the course of 28 days

This is defined as the number of days alive outside of hospital from randomization to Day 28 days.

For a day to be counted as outside of hospital, the subject must not be in hospital. If the subject is in hospital but hospitalization is recorded as not clinically indicated, this day will still be considered as a day in hospital and therefore will not be counted in this endpoint.

The following rules will be applied for missing data:

- If a subject withdraws from the study or is lost to follow up on or prior to Day 28, the days with unknown survival/hospitalization status will be considered as follow:
 - If the subject is discharged from hospital when they withdraw from the study or are lost to follow up, days from last known status to Day 28 (or date last known to be alive if death is known, whichever occurs first) will be counted as days alive and outside of hospital.
 - If a subject is in hospital at the time they withdraw from the study, days from last known status to Day 28 will be assumed hospitalized days.

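### SAP 4.3.2.12 is headed 28 days but its only analysis sentence summarises 90 days, duplicating 4.3.2.13; an apparent copy-paste error

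*SAP*

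**What the plan says.** Protocol Section 3 lists as a secondary endpoint the "Number of days alive outside of hospital from randomization to 28 days after randomization", and lists the 90-day counterpart as a separate item. SAP Table 2 and Table 4 keep the same two entries, and Table 4 assigns each to the full analysis set.

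SAP 3.1.13 derives the 28-day variable: "This is defined as the number of days alive outside of hospital from randomization to Day 28 days". SAP 3.1.14 derives the 90-day variable separately, with its own withdrawal rules.

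The matching analysis section is headed "4.3.2.12 Days alive outside of hospital over the course of 28 days" and has two sentences. The first says that summary statistics "of the days alive outside of hospital over 90 days will be presented by treatment group". The second reads: "The method for handling subjects that withdraw or are lost to follow up on or prior to Day 28 is detailed in Section 3.1.13". Section 4.3.2.13, for the 90-day endpoint, carries the same first sentence and then refers to Day 90 and Section 3.1.14.

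SAP Section 7, on changes of analysis from the protocol, is marked as not applicable.

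**The concern.** The sentence at fault is the instruction from which the table would be programmed. If it is followed to the letter:

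- Sections 4.3.2.12 and 4.3.2.13 produce the same 90-day table, and no endpoint-specific sentence in SAP Section 4 asks for the 28-day one.
- A 90-day summary is paired with a withdrawal rule that stops at Day 28.
- The 28-day result is absent from the primary analysis, which takes place once all subjects have been followed for 38 (±3) days. Endpoints needing 90-day assessments wait for the later update (protocol 9.6, SAP Section 6).
- A programmer who produces the intended 28-day table departs from the literal SAP. SAP 4.1 requires departures from the planned analyses to be detailed in the study report.

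**Working it through.** There is no planned figure to reproduce: the point rests on no sample size, power, error rate or event count. The check compares the texts.

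**Step 1. The window stated at each place.**

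| Place | Window |
|---|---|
| Protocol Section 3, SAP Table 2, SAP Table 4 | 28 days (90-day version listed separately) |
| SAP 3.1.13, derivation | Day 28 |
| SAP 4.3.2.12, heading | 28 days |
| SAP 4.3.2.12, analysis sentence | **90 days** |
| SAP 4.3.2.12, withdrawal rule | Day 28, citing 3.1.13 |
| SAP 4.3.2.13, heading, analysis sentence and withdrawal rule | 90 days, citing 3.1.14 |

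Only the analysis sentence of 4.3.2.12 disagrees with the rest of its row group, and it matches the next section word for word.

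**Step 2. Comparison with a neighbouring section.** SAP 4.3.2.10, on days hospitalized, also has a 28-day heading. Its sentence agrees with it: "of the number of days hospitalized over 28 days will be presented by treatment group". So the SAP's own pattern is for heading and sentence to name the same window.

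**Step 3. Whether the two quantities are interchangeable.** They are not. One is at most 28 and the other at most 90. As an illustration, take a subject last in hospital on Day 8, not readmitted, and alive throughout:

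- over 28 days: 28 − 8 = 20 days
- over 90 days: 90 − 8 = 82 days

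**Step 4. Whether the 28-day result can be read from another planned table.** The nearest is 4.3.2.10. SAP 3.1.11 counts days after death as hospitalized, which by itself would make 28 minus days hospitalized equal to days alive out of hospital. But 3.1.11 counts a hospital day only if hospitalization is clinically indicated, whereas 3.1.13 treats every day in hospital as in hospital. The subtraction therefore overstates the 3.1.13 value by the number of hospital days recorded as not clinically indicated. The 28-day result cannot in general be recovered that way.

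**Step 5. Whether other text covers the 28-day endpoint.** Protocol 9.6.2 says that summary statistics "will be presented by treatment arm for continuous secondary efficacy endpoints (refer to Section 3"), and Section 3 includes this endpoint. SAP 4.1 provides for descriptive statistics on all variables as appropriate. Both are general; neither names this endpoint or its window. The DMC outputs in SAP Table 7 include days alive out of hospital for neither window.

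**Step 6. Extent.** SAP 4.3.2.1 to 4.3.2.16 cover 16 secondary efficacy endpoints. One is affected.

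**The case against.** The strongest reply is that nobody could be misled for long. The heading, the Day 28 withdrawal rule and the pointer to 3.1.13 all say 28 days; one number conflicts, and a programmer would query it. The statistics listed in protocol 9.6.2 are the same ones that 4.3.2.12 names, and SAP Section 7 declares no change from the protocol, so the protocol's analysis stands. The endpoint is purely descriptive: 4.3.2.12 specifies no test, interval or model, and protocol 9.1 states that there is no formal hypothesis testing. The derivation rules in 3.1.13 are complete, so a late correction would lose no data.

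All of this stands, and it sets the severity. It also rules out two stronger inferences that a reader might draw:

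- **That the 28-day endpoint has been dropped, or has no stated analysis.** The documents do not support this. The endpoint remains in the protocol, in SAP Tables 2 and 4 and in 3.1.13, and the general text in protocol 9.6.2 and SAP 4.1 still calls for it to be summarised. What is missing is a correct endpoint-specific sentence.
- **That a 90-day figure is demanded at a time when it cannot exist.** The plan already schedules an updated analysis for endpoints needing 90-day assessments. The only timing effect is that, read literally, the 28-day summary is left out of the primary analysis.

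What the reply does not do is make the sentence right. It is operative text, and it contradicts its own heading and cross-reference.

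**Conclusion.** The inconsistency is real and its severity is low. The endpoint-specific text of the SAP, taken literally, yields two identical 90-day summaries and no 28-day summary at the primary analysis. One descriptive secondary endpoint of 16 is affected. The primary endpoint, the power statement and the safety analyses are not.

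That this is a copying slip rather than a choice is an inference. It rests on the word-for-word match with 4.3.2.13, the 28-day heading and cross-reference in the same section, and the absence of any declared change in SAP Section 7. No sentence in either document says so outright.

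**What to change.** In the first sentence of SAP 4.3.2.12, replace 90 with 28, so that the sentence agrees with its heading, with 3.1.13 and with protocol Section 3. Leave 4.3.2.13 as it is. Record the correction in the SAP amendment history.

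The cost is one number. No data collection, derivation rule or other analysis changes.

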4.3.2.13 Days alive outside of hospital over the course of 90 days

Summary statistics (n, mean, SD, median, minimum and maximum) of the days alive outside of hospital over 90 days will be presented by treatment group.

The method for handling subjects that withdraw or are lost to follow up on or prior to Day 90 is detailed in Section 3.1.14.

4.3.2.14 Relative change from baseline in oxygenation index

Summary statistics (n, mean, median, SD, minimum, and maximum) and the percent change from baseline to each scheduled study assessment will be presented by treatment group.

Box plots of absolute value over time and a line graph of mean change (and SD) from baseline to each scheduled study assessment may be presented for each treatment group.

A by-subject listing will also be presented.

4.3.2.15 Time to clinical improvement of at least 2 points (from randomization) on a 9-point category ordinal scale through Day 28

Time from randomization to the date of first demonstrated clinical improvement of at least 2 points on a 9-point category ordinal scale through Day 28 will be portrayed using the KM method by treatment group.

Alongside summary statistics, a KM plot of the cumulative improvement rate over time will be presented by treatment group.

The HR and its 90% CI will be estimated from a stratified Cox Proportional Hazards model (with ties = Efron), stratified by age (<65 vs ≥65 years) and comorbidities (present vs absent).

The CI will be calculated using a profile likelihood approach. Summary statistics will include the lower and upper quartile and median time to clinical improvement with the 90% CI.

The method for handling subjects that withdraw or are lost to follow up or die is detailed in Section 3.1.16.

In addition to the above, for each treatment group, ordinal scale scores will be presented by day and the change in the score from baseline to each post-baseline assessment will be summarized.

Additional sensitivity analyses may be performed as appropriate.

Time to clinical improvement of at least 2 points (from randomization) on a 9-point category ordinal scale, live discharge from hospital, or considered fit for discharge, whichever comes first) through

Time from randomization to the date of first demonstrated clinical improvement of at least 2 points on a 9-point category ordinal scale, live discharge from hospital, or considered fit for discharge, whichever comes first, through Day 28 will be portrayed using the KM method by treatment group.

Alongside summary statistics, a KM plot of the cumulative improvement rate over time will be presented by treatment group.

The HR and its 90% CI will be estimated from a stratified Cox Proportional Hazards model (with ties = Efron), stratified by age (<65 vs ≥65 years) and comorbidities (present vs absent). The CI will be calculated using a profile likelihood approach. Summary statistics will include the lower and upper quartile and median time to clinical improvement with the 90% CI.

The method for handling subjects that withdraw or are lost to follow up or die is detailed in Section 3.1.16.1.

Additional sensitivity analyses may be performed as appropriate.

Time to recovery (from randomization) through Day 28

Time from randomization to the date of recovery through Day 28 will be portrayed using the KM method by treatment group.

Alongside summary statistics, a KM plot of the cumulative recovery rate over time will be presented by treatment group.

The HR and its 90% CI will be estimated from a stratified Cox Proportional Hazards model (with ties = Efron), stratified by age (<65 vs ≥65 years) and comorbidities (present vs absent). The CI will be calculated using a profile likelihood approach. Summary statistics will include the lower and upper quartile and median time to clinical improvement with the 90% CI.

The method for handling subjects that withdraw or are lost to follow up or die is detailed in Section 3.1.16.2.

Additional sensitivity analyses may be performed as appropriate.

